*ICD-X-CM codes will be translated into local ICD-X codes and provided in SAP

Table 8 in Annex 3). To characterize **maintenance therapy** in the same period, the use of recommended drugs such as oral corticosteroids, immunosuppressants, B-Cell targeting therapies, tocilizumab, eculizumab, satralizumab (Table 9 in Annex 3) and other immunosuppressive treatments (Table 10 in Annex 3) will be retrieved.

The use of pain medications in the 6 months prior to the index date will be determined taking into account drugs specified in Table 11 in Annex 3.

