6.3.3 Treatment patterns

During follow-up, treatment patterns will be characterized in terms of dose, treatment duration, frequency of drug discontinuation, switching and use of add-on therapies. All patients included in the study will be deemed exposed (at least one inebilizumab treatment), but only those with complete 12-month follow-up will be considered in the evaluation of the treatment patterns as described below.

According to the product specifications, the 12-month follow-up will cover 3 potential inebilizumab administrations: initial intravenous (IV) infusion followed by a second

infusion 2 weeks later and a subsequent infusion 6 months after the first treatment (Figure 2A). The first and third infusion will be considered in defining inebilizumab treatment patterns.

Treatment duration will be the sum of days under inebilizumab exposure during the follow-up. Number of days under exposure will be calculated for the first and the third infusion as the difference between end date of inebilizumab exposure period and the administration/prescription/dispensation date (Figure 2B).

[figure not shown]
Inebilizumab complete **exposure period** will be assumed to last 180 days after drug administration/prescription/dispensation. The **end date of the exposure** period will be defined as the end of each inebilizumab exposure period within follow-up or the end date of follow-up if comes first (Figure 2B).

A patient will be considered to be in inebilizumab **continuous use** if no gap longer than 60 days occurs between the end date of the first inebilizumab exposure period and the beginning of the third (2B). **Temporary discontinuation** (intermittent users) will be defined in patients with gaps between inebilizumab exposure periods longer than 60 days but with a subsequent inebilizumab administration/prescription/dispensation during the follow-up. A patient will be defined as having **permanently discontinued** inebilizumab if no subsequent inebilizumab treatment is registered during the follow-up after the end date of the first inebilizumab exposure period.

Switchers will be a subgroup of patients who discontinue inebilizumab (temporarily or permanently) during the follow-up and have other NMOSD maintenance drug administered/ prescribed (Table 9) after the end date of inebilizumab exposure period (2C). The alternative NMOSD drugs will be described.

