The use of **add-on therapies** will be identified by administration/prescription/dispensation of other NMOSD maintenance or other immunosuppressive drug(s) (Table 9 and Table 10) during any of inebilizumab exposure period (2D). Corticosteroid pre-medication before inebilizumab infusion (used to reduce potential infusion reactions) will not be considered as an add-on therapy.

Figure 2 Inebilizumab treatment patterns

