6.4.2 Germany

German Government Health Insurance (*Gesetzliche Krankenversicherung* [GKV]) claims from approximately 8-10 different statutory health insurance providers (SHIs) are collected by Team Gesundheit. This is an established research institute which has been working for more than 1000 health insurance companies, companies and ministries since 1997. With branches in Essen, Hamburg, Bielefeld, Berlin, Frankfurt and Munich they are active in German health management nationwide. Since an SHI is a requirement for individuals with a permanent place of residence in Germany, even for short-term stays, the general population coverage in the SHI is considered nationwide. The SHIs also allow insurance coverage for children and spouses within a family insurance policy. The population size available through Team Gesundheit is approximately 5 million individuals which represents an estimated 6.9% of the SHI-insured population in Germany. Available data history through collaboration with Team Gesundheit reaches back to January 2008. Since 2012 all individuals in Germany have lifelong specific ID and SHI numbers which would not change throughout lifetime.

The database contains information from primary care, in- and out-patient hospital care as well as sick leaves. Relevant measures are available in the German database allowing demographic characteristics, treatments, healthcare utilization and clinical outcomes to be assessed, for example:

- registration data including age, gender;
- out-patient care data including ICD-10 diagnoses (not granular and per quarter), physician specialty
- inpatient care claim including ICD-10 diagnoses (up to 3 principal and 30 secondary diagnoses per stay), billed diagnosis-related group (German classification), up to 30 OPS-Codes per stay, duration of hospitalizations, and medical department; drug prescription data including ATC codes of prescribed medications

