	6A551Z3 - Pheresis of Plasma, Multiple	ICD-10-PCS
	8-820 Therapeutic plasmapheresis	OPS

Abbreviations: ATC, Anatomical therapeutic chemical; ICD-10: 10th Revision of International Classification of Diseases; OPS, operation and procedure classification system, PCS, Procedure Coding System

* Only intravenous administrations

Table 9 NMOSD Maintenance Therapies

Name of Agent	Description	Coding
1. Oral Steroids	H02 - Corticosteroids for systemic use	ATC
2. Immunosuppressive therapies		
a. Azathioprine	L04AX01	ATC
b. Mitoxantrone	L01DB07	ATC
c. Mycophenolate Mofetil	L04AA06	ATC
d. Methotrexate	L01BA01; L04AX03	ATC
e. Cyclophosphamide	L01AA01	ATC
3. B-Cell Targeting Therapy (anti-CD20)		
a. Ocrelizumab	L04AA36 /L04AG08 from 2024	ATC
	6-00a.e Atezolizumab, parenteral	OPS
b. Ofatumumab	L04AA52/ L04AG12 from 2024	ATC
	6-006.4 Ofatumumab, parenteral	OPS
c. Rituximab	L01FA01	ATC
	6-001.h Rituximab, intravenously	OPS
	6-001.j Rituximab, subcutaneous	
4. Tocilizumab	L04AC07	ATC
	6-005.m Tocilizumab, intravenously	OPS
	6-005.n 8 Tocilizumab, subcutaneous	
5. Eculizumab	L04AA25/L04AJ01 from 2024	ATC
	6-003.h Eculizumab, parenteral	OPS
6. Satralizumab	L04AC19	ATC

Abbreviations: ATC, Anatomical therapeutic chemical; NMOSD, Neuromyelitis optica spectrum disorder; OPS, operation and procedure classification system

Table 10 Other Immunosuppressive Drugs of Interest

Name of Agent	Description	Coding
1. Interferon beta-1a and 1b	L03AB07; L03AB08	ATC
2. Dimethyl-fumarate	L04AX07; L04AX09	ATC
3. Alemtuzumab	L04AA34/L04AG06 from 2024	ATC
	6-001.0 Alemtuzumab, parenteral	OPS
4. Fingolimod	L04AA27/L04AE01 from 2024	ATC
5. Natalizumab	L04AA23/L04AG03 from 2024	ATC
	6-003.f Natalizumab, parenteral	OPS
6. Glatiramer acetate	L03AX13	ATC
7. Peginterferon beta-1a	L03AB13	ATC
8. Teriflunomide	L04AA31/L04AK02 from 2024	ATC
9. Bortezomib	L01XG01	ATC
	6-001.9 Bortezomib, parenteral	OPS
10. Cladribine	L01BB04; L04AA40	ATC
	6-00a.4 Cladribine, oral	OPS
11. Daclizumab	L04AC0	ATC
	6-009.9 Daclizumab, parenteral	OPS
12. Ozanimod	L04AA38/L04AE02 from 2024	ATC
13. Siponimod	L04AA42/L04AE03 from 2024	ATC
14. Tacrolimus	L04AD02	ATC

Abbreviations: ATC, Anatomical therapeutic chemical; OPS: operation and procedure classification system

Table 11 Pain Medication

Name of Agent	Description	Coding
1. Anti-inflammatory and antirheumatic drugs	M01	ATC
2. Topical products for joint and muscular pain	M02	ATC
3. Muscle relaxants	M03	ATC
4. Anesthetic drugs	N01	ATC
5. Analgesics	N02	ATC

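### A single short oral steroid course counts as add-on therapy or as a switch, because Table 9 takes ATC H02 with no rule for sustained use

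*Protocol*

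**What the plan says.** Annex 3 of the protocol gives the same code, "H02 - Corticosteroids for systemic use", to two agents. In Table 8 (acute treatments) it stands for intravenous corticosteroids, with the footnote "Only intravenous administrations". In Table 9 (maintenance therapies) it stands for the row "1. Oral Steroids", which has no footnote on route, number of records or duration. Section 6.3.2 agrees with that row name: it describes maintenance therapy as "the use of recommended drugs such as oral corticosteroids, immunosuppressants, B-Cell targeting therapies" and others.

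Section 6.3.3 then uses Table 9 in two rules:

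- **Add-on** is identified by "administration/prescription/dispensation of other NMOSD maintenance or other immunosuppressive drug(s) (Table 9 and Table 10) during any of inebilizumab exposure period".
- **Switchers** are a subgroup of "patients who discontinue inebilizumab (temporarily or permanently) during the follow-up" who have a Table 9 drug recorded after the exposure period ends.

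One steroid exclusion is written, for add-on only: "Corticosteroid pre-medication before inebilizumab infusion (used to reduce potential infusion reactions) will not be considered as an add-on therapy".

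Section 6.7.2.2 measures time to switch and time to add-on up to the first recorded start of such a drug. Section 6.7.2 defines the concomitant-immunosuppressant subgroup by Tables 9 and 10.

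**The concern.** Systemic steroids can be given as a short course or as long-term maintenance. The code list separates the two uses by route, but the add-on and switch rules need them separated by duration. An oral course of a few days and continuous oral maintenance are both oral H02 records, and one record is enough under either rule.

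Add-on use and switching are objective 2 results. A short course would be reported as augmentation or as a change of maintenance drug, and its date could become the time to that event. Through the subgroup definition the problem also reaches the subgroup analyses of objectives 1 and 3, including incidence of adverse events of special interest (AESI).

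The pre-medication exclusion shows that the authors saw steroids could contaminate the add-on count. It closes one pathway and is not carried over to switching. An oral pre-medication record dated shortly before a delayed third infusion falls after the first exposure period and before the next. In a patient with temporary discontinuation, that record meets the switch rule.

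**Working it through.** The protocol gives no figure that depends on this point, so there is nothing to reproduce. Two checks follow.

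**1. On how many follow-up days does a Table 9 steroid record count?**

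Inputs from section 6.3.3: exposure lasts 180 days from the first and from the third infusion; a gap longer than 60 days is discontinuation; add-on means a record during exposure; switch means a record after exposure in a discontinuer. Assumption: 12 months is 365 days, numbered 1 to 365.

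- Third infusion on day 180: exposed on days 1–360, so add-on on 360 days. The last 5 days count as neither.
- Third infusion on day 240 (gap 60, still continuous): 180 + (365 − 240 + 1) = 306 exposed days. Days 181–239 (59 days) count as neither.
- Third infusion on day 300 (gap 120, temporary discontinuation): 180 + (365 − 300 + 1) = 246 exposed days. Days 181–299 (119 days) count as switch.
- No third infusion (permanent discontinuation): 180 exposed days. Days 181–365 (185 days) count as switch.

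| Third infusion | Add-on | Switch | Neither |
|---|---|---|---|
| Day 180 | 360 (98.6%) | 0 | 5 (1.4%) |
| Day 240 | 306 (83.8%) | 0 | 59 (16.2%) |
| Day 300 | 246 (67.4%) | 119 (32.6%) | 0 |
| None | 180 (49.3%) | 185 (50.7%) | 0 |

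In a discontinuer, a record classed as a Table 9 steroid counts on every day of follow-up. In these two continuous-use cases it counts on about 84% to 99% of days, and only as add-on.

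**2. How far could the add-on proportion move?**

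The protocol gives no frequency of steroid courses, so all inputs here are assumptions. Let *a* be the true add-on proportion, *r* the share of patients with a short steroid course, and *c* the fraction of those courses captured as Table 9 records, with courses independent of true add-on use:

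apparent add-on = *a* + (1 − *a*) × *r* × *c*

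With *a* = 20% and *r* from 5% to 20%:

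- *c* = 1: 0.20 + 0.80 × 0.05 = 24%, up to 0.20 + 0.80 × 0.20 = 36%
- *c* = 0.5: 0.20 + 0.80 × 0.05 × 0.5 = 22%, up to 0.20 + 0.80 × 0.20 × 0.5 = 28%
- *c* = 0: 20%, no inflation

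The added term, (1 − *a*) × *r* × *c*, is the share of patients who count as add-on only because of a captured short course.

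**The case against.** The strongest reply is that Table 9 does restrict route. Its row is named for oral steroids and section 6.3.2 says the same, so an intravenous course belongs to Table 8, which feeds neither add-on nor switching. That is correct. A reader might infer from the shared code that every steroid course given for a relapse is counted as add-on or as a switch. The document does not support this. The treatment-based relapse markers in section 6.3.2 name intravenous steroids, not oral ones.

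Nor is it shown that sources lack the means to tell the routes apart. PHARMO's GP and pharmacy records list route, and SNDS lists brand name. For Germany, section 6.4.2 mentions "drug prescription data including ATC codes of prescribed medications", but that list is offered as examples, so missing route information cannot be inferred from it. Section 6.4.1 says the only in-hospital prescriptions captured in the French data are expensive drugs, so an ordinary inpatient steroid course would mostly be unseen rather than miscounted.

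A reader might also infer the reverse error, with oral maintenance steroids entering the baseline acute treatments. The Table 8 footnote bars that.

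A further reply is that section 6.7.1 leaves full variable definitions to the SAP. Route look-ups and local product codes can indeed wait for it. But the protocol already fixes the one-record rules and the code list, and a SAP that follows them faithfully inherits the problem.

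Finally, section 6.3.3 says the alternative drugs will be described, so a switch to a steroid alone would be visible. That helps the reader of the switch results, but it does not correct the proportion or the time to switch.

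**Conclusion.** The point holds for short oral courses. Under the rules as written, one oral H02 record other than pre-medication is add-on therapy during exposure, and any one such record after exposure ends is a switch in a patient who discontinued. This does not depend on the quality of route data. For intravenous courses the problem is conditional: it arises only in a source where neither route nor product can be identified, and the protocol does not establish that any source is in that position.

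The size is unknown. Inflation of the add-on proportion lies between zero and the share of patients whose only Table 9 or 10 record is a short steroid course. The 4 to 16 percentage points at full capture shown above (20% to 24–36%) rest on assumed inputs and are not a prediction. For switching, the patient must also have discontinued; within that group a single short course after exposure ends is enough to change the classification.

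The change is worth making: the affected quantities are objective 2 results and a subgroup used for all objectives, and the repair is cheap.

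**What to change.** - In Table 9, row 1, restrict H02 to oral products identified by route, brand or local product code.
- In section 6.3.3, apply the pre-medication exclusion to switching as well as to add-on.
- Require evidence of sustained use before H02 counts as maintenance, add-on or switch. At least two records at least 28 days apart would be one form; the threshold is illustrative and for the sponsor to set.
- Report add-on, switching, their times and the concomitant-immunosuppressant subgroup with and without H02 in every source. Doing this everywhere, rather than dropping H02 in selected sources, keeps the definition the same across countries.

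The cost is a code-list edit, a sentence or two in section 6.3.3, and an extra column in the affected tables; no new data are needed. The downside is small: a true new oral maintenance steroid with only one record in follow-up is not counted in the restricted version.

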6.4.4 Italy

The Italian Multiple Sclerosis & Related Disorders Register (*Registro Italiano Sclerosi Multipla e Patologie Correlate* [RISM]) was officially established in 2015. As of February 2023, the register was actively covering 133 MS centers, corresponding to a total of 80,353 patients, of which 273 are diagnosed with NMOSD. Since July 2022, the

register comprises a module for the collection of information on NMOSD, and has projects dedicated to NMOSD patients (22). Nonetheless, data on NMOSD patients were collected previous to 2022, without a specific module implemented. The data are collected from participating centers through a web-based system developed for the study, available at the IMS&RD website. Data are collected from accrual to exit of database, which may occur at date of death, when patient moves to a center outside of the covered network or withdraws their consent to participate. The data are centrally monitored to ensure quality of data, completeness, accuracy, and consistence (23). Requests to access the data are evaluated by the Scientific Committee, composed by clinicians, methodologists, representatives of MS centers, and of the Italian Neurological Society (23).

To ensure the collection of sufficient data for the clinical characterization of the single patient mandatory variables collected by the register include patient identification, demographics, vital status, disease onset date, diagnosis date, relapses, treatments and severe adverse events. This minimum dataset may be completed with an extension to optional information on family history, comorbidities, laboratory tests and MRI. Furthermore, the register has data on patient's unique personal identifier, to avoid inclusion of the same patient by more than 1 center. Diagnosis information is available and captured with ICD-9-CM coding system.

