ANNEX 3. ADDITIONAL INFORMATION

Table 6 List of Comorbidities

Comorbidities	Diagnosis ICD-9-CM Codes*	Diagnosis ICD-10-CM Codes*
Coronary heart disease	410.xx, 411.xx, 412, 413.x, 414.xx	I21.xx, I24.x, I25.2, I20.x, I25.xxx
Heart failure	398.91, 402.01, 402.11, 402.91, 404.01, 404.03, 404.11, 404.13, 404.91, 404.93, 428.xx	I09.81, I11.0, I13.0, I13.2, I50.xx
Cerebrovascular disease	430, 431, 432.x, 433.xx, 434.xx, 435.x, 436, 437.0, 437.1, 437.8, 437.9, 438.xx, 997.02	I60.9, I61.9, I62.xx, I63.xx, I65.xx, I66.xx, G45 [excl. G45.4], I67.84, I67.2, I67.81, I67.82, I67.89, I67.9, I69.8, I69.9x, I97.81, I97.82
Lung disease	493.00-493.02, 493.10-493.12, 493.20-493.22, 493.81, 493.82, 493.90-493.92, 491.0, 491.1, 491.20-491.22, 491.8, 491.9, 492.0, 492.8, 496, 490, 494.0, 494.1, 495.0-495.9, 500, 501, 502, 503, 504, 505, 506.4	J45.2x-J45.5x, J45.9xx, J41.x, J42, J43.x, J44.x, J60, J61, J62.x, J63.x, J64, J65, J66.x, J67.x, J68.4
Renal disease	403.01, 403.11, 403.91, 404.02, 404.03, 404.12, 404.13, 404.92, 404.93, 582.x, 583.0-583.7, 585.x, 586, 588.xx, V42.0, V45.1x, V56.x	I12.0, I13.11, I13.2, N03.x, N05.9, N05.2, N05.5, N17.1, N18.x, N19, N25.xx, Z94.0, Z99.2, Z91.15, Z49.xx
Rheumatic disease	446.5, 710.0-710.4, 714.0-714.2, 714.81, 725	M31.5, M31.6, M32.xx, M34.xx, M35.0x, M33.xx, M05.xxx, M35.3
Diabetes	249.xx, 250.xx, 357.2, 362.0x, 366.41, 648.0, E932.3, V58.67	E08.xx, E09.xx, E10.x, E11.xx, E13.xx, O24 [excl. O24.4], Z79.4
Hypertension	401.x, 402.xx, 403.xx, 404.xx, 405.xx	I10, I11.x, I12.x, I13.xx, I15.x, I16.x
Malignancy	140.x-171.x, 174.x-195.x, 200.x- 207.x, 209.0x - 209.3x, 173.00, 173.09, 173.10, 173.19, 173.20, 173.29, 173.30, 173.39, 173.40, 173.49, 173.50, 173.59, 173.60, 173.69, 173.70, 173.79, 173.80, 173.89, 173.90, 173.99, 796.76, 795.06, 795.16	C00.x-C43.x, C4A.x, C45.x- C96.x, C44.00, C44.09, C44.10x, C44.19x, C44.20x, C44.29x, C44.30x, C44.39x, C44.40, C44.49, C44.50x, C44.59x, C44.60x, C44.69x, C44.70x, C44.79x, C44.80x, C44.89, C44.90, C44.99, R85.614, R87.614, R87.624
Osteoporosis	733.0x, 733.1x	M80.xxxx, M81.x
Anxiety	300.2x, 300.0x, 300.3	F40.xxx, F41.x, F42.x
Depression	296.21, 296.22, 296.23, 296.26, 296.31, 296.32, 296.33, 296.36	F32.x, F33.xx
Skin ulcers/cellulitis	681.00, 681.10, 681.9, 682.x, 707.xx	L03.01x, L03.03x, L03.11x, L03.21x, L03.31x, L03.81x, L03.90, L89.x, L97.x

Comorbidities	Diagnosis ICD-9-CM Codes*	Diagnosis ICD-10-CM Codes*
Renal transplantation	55.69, V42.0	Z94.0

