Infections	Available upon request	Available upon request

Abbreviations: ICD-9/ICD-10, 9th/10th Revision of International Classification of Diseases; CM, Clinical Modification
*ICD-X-CM codes will be translated into local ICD-X codes and provided in SAP

Table 7 NMOSD-Associated Conditions

NMOSD-associated Conditions	Diagnosis ICD-9-CM Codes*	Diagnosis ICD-10-CM Codes*
Hypothyroidism	244.x	E89.0, E03.2, E03.8, E03.9
Pernicious anemia	281.0, 281.1	D51.x
Ulcerative colitis	556.x [excl. 556.2 and 556.3]	K51.xx [excl. K51.2x and K51.3x]
Myasthenia gravis	358.0x	G70.0x
Idiopathic thrombocytopenic purpura	446.6	M31.1
Hemiplegia/paraplegia	334.1, 342.x, 343.x, 344.0x-344.6x, 344.9	G11.4, G81.xx, G80.x, G83.0, G83.1x, G83.2x, G83.3x, G83.4, G83.9, G82.xx
Bladder dysfunction	788.30, 788.31, 788.33, 788.34, 788.36, 788.37, 788.39-788.43, 596.xx	N30.xx, N31.x, N32.xx, N33
Neuropathic pain	353.x, 354.x, 355.x, 356.x, 357.x, 250.6, 729.2, 782	E08.40-E08.42, E09.40, E09.42, E10.40-E10.42, E11.40-E11.42, E13.40-E13.42, G50.0, G50.1, G54.x, G55.x, G56.x, G57.x, G58.x, G60.x, G61.x, G62.x, G63, G64, G65.x, G90.5x, M05.5x, M79.2, M54.1, R20
Antiphospholipid syndrome	289.81	D68.61
Sarcoidosis	135	D86.xx
Scleroderma	357.4, 359.6, 517.2, 701.0, 710.1	M34.xx, L90.0, L94.0, L94.1, L94.3
Sjogren's syndrome	710.2	M35.0x
Systemic lupus erythematosus	710	M32.xx
Dorsalgia	724.5	M54
Disorders of lipoprotein metabolism and other lipidemias	272.0, 272.1, 272.2, 272.3, 272.4, 272.5, 272.9	E78
Other acute disseminated demyelination	341.9	G36.9
Disorders of refraction and accommodation	367	H52
Visual disturbances	368	H53
Disturbances of skin sensation	782	R20
Somatoform disorders	300.81	F45
Other dorsopathies, not elsewhere classified	723.2, 723.3, 723.8, 723.9	M53

NMOSD-associated Conditions	Diagnosis ICD-9-CM Codes*	Diagnosis ICD-10-CM Codes*
-----------------------------	------------------------------	-------------------------------

Abbreviations: ICD-9/ICD-10, 9th/10th Revision of International Classification of Diseases; CM, Clinical Modification; NMOSD, Neuromyelitis optica spectrum disorder

*ICD-X-CM codes will be translated into local ICD-X codes and provided in SAP

Table 8 Acute Treatments

Name of Agent	Description	Coding
Intravenous Corticosteroids*	H02 - Corticosteroids for systemic use	ATC
Intravenous Immunoglobulin (IVIG)*	J06B - Immunoglobulins	ATC
	8-810.w Human immunoglobulin, polyvalent	OPS
Plasma Exchange (PLEX)	6A550Z3 - Pheresis of Plasma, Single	ICD-10-PCS

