		787.7	R19.5	
		787.99		
	Pyrexia	780.60	R50 R50.2 R50.8 R50.9	
		Chills	780.64	R68.8
		Fatigue	780.79	R68.8
		Chest discomfort	786.5	R07
	786.50		R07.3	
786.59	R07.4			
Pain	Pain, not elsewhere classified	R52 R52.0 R52.9		
	Acute pain			
Back pain	724.5	M54.9		
Myalgia	729.1	M79.1		

Classification	Conditions	Diagnosis ICD-9 -CM Codes*	Diagnosis ICD-10-CM Codes*
	Headache	784.0	R51
	Dysgeusia	781.1	R43.2
	Dizziness	780.4	R42
	Dyspnea	786.05	R06.0
	Oropharyngeal pain	784.1	R06.0
	Cough	786.2	R05
	Rash	782.1	R21
	Urticaria/ Erythema	708 708.9 782.9	R23 R23.8 L50 L50.9
	Pruritus	782.1 698	R21
	Rash pruritic	782.1	R21
	Flashing	782.62	R23.2
Infusion related reactions	Generalized skin eruption due to drugs and medicaments	693.0	L27.0
	Localized skin eruption due to drugs and medicaments	-	L27.1
	Complications following infusion, transfusion and therapeutic injections	999.34 999.39	T80
	Other complications following infusion, transfusion and therapeutic injection	999.88 999.89	T80.8
	Unspecified complication following infusion, transfusion and therapeutic injection	999.80	T80.9
	Anaphylactic shock due to adverse effect of correct drug or medicament properly administered	999.4	T88.6
	Unspecified adverse effect of drug or medicament	995.20 995.29	T88.7
	Anaphylactic shock, unspecified	995.0	T78.2
	Angioneurotic oedema	995.1	T78.3

Classification	Conditions	Diagnosis ICD-9 -CM Codes*	Diagnosis ICD-10-CM Codes*
	Allergy, unspecified	995.3	T78.4
	Shock, not elsewhere classified		R57
	Other shock	785.59	R57.8
	Shock, unspecified	785.50	R57.9
Malignancies		140-209	C00-C96

Abbreviations: ICD-9/ICD-10: 9th/10th Revision of International Classification of Diseases, CM, Clinical Modification.

*ICD-X-CM codes will be translated into local ICD-X codes and provided in SAP

#captured if leading to infection-related in-patient hospitalization during the follow-up

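### Four code entries in Annex 3 conflict with the protocol's own tables and could misclassify patients if carried into the SAP unchecked

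*Protocol*

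**What the plan says.** Section 6.3 defines diagnoses by ICD-9 or ICD-10 codes and medications by ATC or OPS codes; Annex 3 lists them.

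- **Ocrelizumab (Table 9).** The ATC entry is "L04AA36 /L04AG08 from 2024". The OPS line beneath it reads "6-00a.e Atezolizumab, parenteral". The next agent's OPS line is "6-006.4 Ofatumumab, parenteral", which names its own row.
- **SLE (Table 7).** "Systemic lupus erythematosus" has the ICD-9-CM code 710 and the ICD-10-CM code M32.xx. In Table 6 the rheumatic disease row begins "446.5, 710.0-710.4, 714.0-714.2".
- **Daclizumab (Table 10).** The ATC code is printed as L04AC0. The OPS entry is "6-009.9 Daclizumab, parenteral".
- **Serious infections (Table 12).** The ICD-10 list for meningitis/encephalitis contains B262.2. Table 2 has B26.2 among the parainfectious disorders.

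The lists are used as follows. Tables 9 and 10 describe baseline maintenance and other immunosuppressive therapy (section 6.3.2), add-on use (section 6.3.3) and the subgroup on concomitant immunosuppressants (section 6.7.2). Table 9 alone defines switching (section 6.3.3). Table 7 supplies the associated conditions described at baseline. Table 12 supplies the safety outcomes (section 6.3.4).

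**The concern.** These entries decide who is counted as having a condition or receiving a drug. A code that points to another drug, takes in neighbouring conditions or matches nothing changes the counts without any error message. The study is descriptive and has no control group in which such an error could cancel. Its planning figure is a pooled cohort of 400 (section 6.5), so a few misassigned patients can shift a switching, add-on or subgroup proportion.

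Footnotes to Tables 6, 7 and 12 promise translation of the ICD codes into local codes in the SAP. Translating a wrong source code reproduces the error unless someone notices it. Tables 9 and 10 carry no such footnote.

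**Working it through.** The plan states no figure to reproduce on this point. The check compares entries within the protocol and sizes the reach from Table 4.

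**1. Ocrelizumab OPS line.** Tables 9 and 10 contain 12 OPS lines: seven in Table 9 (ocrelizumab 1, ofatumumab 1, rituximab 2, tocilizumab 2, eculizumab 1) and five in Table 10 (alemtuzumab, natalizumab, bortezomib, cladribine, daclizumab). Eleven name the agent of their row; the ocrelizumab line does not. Atezolizumab appears nowhere else in the protocol. A complete wrong drug name is not a plausible PDF-reading loss. Two readings remain:

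- The code is atezolizumab's, as labelled. Ocrelizumab is then missed through OPS, and atezolizumab would count as maintenance therapy.
- The code is ocrelizumab's and only the label is wrong. Nothing is then misclassified.

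The protocol cannot settle which is true.

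OPS is the coding of the German source (section 6.4.2). Germany's share of Table 4 is:

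- lower bound, 2006 criteria: 26 / 576 = 4.5%
- upper bound, 2006 criteria: 220 / 4,870 = 4.5%

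If inebilizumab uptake followed Table 4 (an assumption), a cohort of 400 would hold about 400 × 26 / 576 = 18 German patients. Only those whose ocrelizumab use is visible solely through OPS would be affected.

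**2. SLE in ICD-9-CM.**

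| Condition (Table 7) | ICD-9-CM | ICD-10-CM |
|---|---|---|
| SLE | 710 | M32.xx |
| Scleroderma | 710.1 (among others) | M34.xx (among others) |
| Sjogren's syndrome | 710.2 | M35.0x |

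Table 6 uses 710.0 to 710.4, so in the protocol's own usage 710 is a category with fourth digits. Read as a parent code, 710 takes in 710.1 and 710.2, and patients with scleroderma or Sjogren's syndrome are also counted as SLE. Matched exactly, it misses every case recorded with a fourth digit. The first reading over-counts and the second under-counts. The ICD-10 column keeps the three conditions apart, so the two columns do not define the same condition.

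Section 6.4.4 says diagnoses in the Italian register are "captured with ICD-9-CM coding system". No other source is described that way.

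**3. Daclizumab ATC code.** Tables 9 and 10 hold 15 + 23 = 38 drug-level ATC codes. Of these, 37 have seven characters and one, L04AC0, has six. Matched exactly, it equals no seven-character code, so daclizumab is missed through ATC. Matched as a prefix, it captures tocilizumab (L04AC07 in Table 9).

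**4. B262.2.** In the meningitis/encephalitis row, the ICD-9 column has 072.1 and 072.2, while the ICD-10 column has B26.1 and B262.2. With B26.2 in Table 2, the intended entry is evident. As printed, the string does not have the form of the other ICD-10 codes and would not match a record coded B26.2.

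**The case against.** The strongest reply is that the operational lists are deferred. Section 6.3.2 leaves detailed definitions and local codes to the SAP, and section 6.7.1 commits the SAP to full definitions of exposures, outcomes, covariates and subgroups. On this view the faults are typographical and would be caught there. That they are probably typographical stands. Deferral does not answer entries that the protocol already states, and states inconsistently, because the SAP lists will be built from them.

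Several limits on reach also stand. The ocrelizumab row keeps its ATC codes, and the German source has prescription data with ATC codes. The short daclizumab code may be a loss in PDF reading, and its OPS code is intact. If it is matched as a prefix, the drug captured is already in Table 9, so add-on use and the subgroup, which pool both tables, do not change; only the drug-level description would. The bare 710 may be 710.0 with a lost trailing zero. Comorbidities in the Italian register are optional data.

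A reader might infer more than the documents support:

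- **No German hospital ocrelizumab would be found and every OPS hit would be the wrong drug.** This assumes the code, not the label, is wrong.
- **The fault in Table 10 affects switching.** Switching is defined by Table 9 alone.
- **The SLE fault touches the whole Italian share of Table 4 (208 / 576 = 36%).** That is a share of expected NMOSD patients, not of inebilizumab users with recorded comorbidities. The register held 273 NMOSD patients in February 2023.
- **Neuropathic pain must lose 782 and R20 because disturbances of skin sensation uses the same codes.** Table 7 conditions are not stated to be mutually exclusive, so this is largely a case-definition choice.
- **"Oropharyngeal pain" sharing R06.0 with dyspnea distorts the safety results.** Safety events are analysed by category, so the repetition has little effect.

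**Conclusion.** The point holds as an internal inconsistency that could misclassify patients, not as one shown to do so. The ocrelizumab line and the SLE code are the firmest items. The first disagrees with its own row; the second fails whether read as a parent or matched exactly. B262.2 is a plain misprint limited to one code in the serious-infection list. The daclizumab code is the weakest, since it may not be in the source document at all.

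The effect on results is likely to be small. The ocrelizumab line reaches baseline maintenance therapy, switching, add-on use and the immunosuppressant subgroup, but only through OPS in a source holding about 4.5% of expected patients. The SLE code reaches one baseline condition in one source with optional comorbidity data. The documents give no prevalence of these conditions and no frequency of ocrelizumab use in the cohort, so no misclassification rate can be stated. Correction is still worthwhile because it costs almost nothing and is easiest before the SAP lists are built.

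**What to change.** Amend Annex 3 as follows:

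1. Check the ocrelizumab OPS line in Table 9 against the OPS catalogue and correct the code or the label, whichever is wrong.
2. In Table 7, replace 710 with 710.0 for SLE, confirming it in the ICD-9-CM catalogue.
3. Check the daclizumab ATC code in the source file and complete it if it is short there too.
4. In Table 12, replace B262.2 with B26.2.
5. Check all Annex 3 lists against the source catalogues before local translation, and state for each code whether it is matched exactly or as a prefix.

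The cost is a few table edits and one pass through the catalogues. No objective, design feature or analysis changes.
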